	Never	0	1	2	3	4	5	6	7	8	9	10	Worst Pain Imaginable
	\bigcirc												R
													\smile
4. D	uring the	past 4 we	eeks, or si	nce your	injury, ho	w stiff or s	swollen w	vas your k	nee?				
	Not at	all		Aildly		Moder	ately	[Very		E	xtremely	/
5. W	 5. What is the highest level of activity you can perform without significant swelling in your knee? Very strenuous activities like jumping or pivoting as in basketball or soccer Strenuous activities like heavy physical work, skiing or tennis Moderate activities like moderate physical work, running or jogging Light activities like walking, housework, or yard work Unable to perform any of the above activities due to knee swelling 												
_]Yes	No		liee your .			• 10 • 11 01						
7. W	_	•			^		0			your kneef	2		
L	Very strenuous activities like jumping or pivoting as in basketball or soccer												
	Strenuous activities like heavy physical work, skiing or tennis												
	Moderate activities like moderate physical work, running or jogging												
	Light activities like walking, housework or yard work Unable to perform any of the above activities due to giving way of the knee												
	_]Unable	to perfor	m any of	the above	e activities	due to gi	ving way	of the kne	ee				

CARTISTEM®

page 52 of 137

IKDC Subjective Knee Evaluation Form cont.

SPORTS ACTIVITIES:

8. What is the highest level of activity you can participate in on a regular basis?

Very strenuous activities like jumping or pivoting as in basketball or soccer

Strenuous activities like heavy physical work, skiing or tennis

Moderate activities like moderate physical work, running or jogging

Light activities like walking, housework or yard work

Unable to perform any of the above activities due to knee

9. How does your knee affect your ability to:

		Not difficult at all	Minimally difficult	Moderately Difficult	Extremely difficult	Unable to do
a.	Go up stairs					
b.	Go down stairs					
c.	Kneel on the front of your knee					
d.	Squat					
e.	Sit with your knee bent					
f.	Rise from a chair					
g.	Run straight ahead					
h.	Jump and land on your involved leg					
i.	Stop and start quickly					

FUNCTION:

10. How would you rate the function of your knee on a scale of 0 to 10 with 10 being normal, excellent function and 0 being the inability to perform any of your usual daily activities which may include sports?

FUNCTION PRIOR TO YOUR KNEE INJURY:

Cannot perform	0	1	2	3	4	5	6	7	8	9	10	No limitation
daily activities												
CURRENT FUNCTION OF YO	UR K	NEE:										
Cannot perform	0	1	2	3	4	5	6	7	8	9	10	No limitation
daily activities												

CARTISTEM®

page 53 of 137

APPENDIX 2. LYSHOLM SCORE

LYSHOLM KNEE SCORING SCALE

Instructions: Below are common complaints which people frequently have with their knee problems. Please check the statement which best describes your condition.

I.	LIMP:	V.	PAIN:
	I have no limp when I walk. (5)		I have no pain in my knee. (25)
	I have a slight or periodical limp when I walk. (3)		I have intermittent or slight pain in my knee
	I have a severe and constant limp when I walk. (0)		during vigorous activities. (20)
		_	I have marked pain in my knee during vigorous activities. (15)
II.	USING CANE OR CRUTCHES		I have marked pain in my knee during or after
	I do not use a cane or crutches. (5)		walking more than 1 mile. (10)
	I use a cane or crutches with some		I have marked pain in my knee during or after
	weight-bearing. (2)	_	walking less than 1 mile. (5)
	Putting weight on my hurt leg is impossible. (0)		I have constant pain in my knee. (0)
		VI.	SWELLING
III.	LOCKING SENSATION IN THE KNEE		I have no swelling in my knee. (10)
	I have no locking and no catching sensations in my knee. (15)	_	I have swelling in my knee only after vigorous activities. (6)
	I have catching sensation but no		I have swelling in my knee after ordinary
	locking sensation in my knee. (10)		activities. (2)
	My knee locks occasionally. (6)		I have swelling constantly in my knee. (0)
	My knee locks frequently. (2)		
	My knee feels locked at this moment. (0)		
	•	VII.	CLIMBING STAIRS:
IV.	GIVING WAY SENSATION FROM THE KNEE		I have no problems climbing stairs. (10)
	My knee never gives way. (25)		I have slight problems climbing stairs. (6)
	My knee rarely gives way, only during athletics or		I can climb stairs only one at a time. (2)
	other vigorous activities. (20)		Climbing stairs is impossible for me. (0)
	My knee frequently gives way during athletics or		• · · · · · · · · · · · · · · · · · · ·
	other vigorous activities, in turn I am unable to	VIII.	SQUATTING
	participate in these activities. (15)		I have no problems squatting. (5)
	My knee occasionally gives way during daily		I have slight problems squatting. (4)
	activities. (10)		I can not squat beyond a 90 degree bend in my
	My knee often gives way during daily activities. (5)		knee. (2)
	My knee gives way every step I take. (0)		Squatting is impossible because of my knee. (0)
	my mice grees may every step i take. (6)		squaring is impossible because of my knee. (6)

TOTAL___/100

INSTRUCTIONS: Please place an X on the line to indicate the amount of pain you have had in your knee(s) the past 24 hours. The scale ranges from "no pain at all" to the "worst possible pain".

CARTISTEM®

page 54 of 137

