6.2 Subject Selection Criteria

- 1) Inclusion Criteria
- A. Patients with an intended- to- treat single focal, full-thickness cartilage defect (ICRS [International Cartilage Repair Society] Grade 3 or 4) of the knee as a result of ageing,

CARTISTEM®

page 19 of 137

CONFIDENTIAL: These all contents herein are the sole property of MEDIPOST Co., Ltd. Any reproduction or distribution of this document without the written consent of MEDIPOST Co., Ltd is prohibited. Copyright © 2017 MEDIPOST Co., Ltd.

trauma, or degenerative diseases

- B. Age \geq 18 years old
- C. Size of the articular cartilage lesion is $\ge 2 \text{ cm}^2$
- D. Swelling, tenderness and active range of motion \leq Grade II
- E. Joint pain : 20-mm 60-mm on VAS (Visual Analog Scale) at the time of Screening
- F. Appropriate blood coagulation, kidney and liver function laboratory parameters:
 - ✓ PT(INR) < 1.5, APTT <1.5×control
 - ✓ Creatinine \leq 2.0 mg/dL, Albumin \leq trace in urine dipstick test
 - ✓ Bilirubin \leq 2.0 mg/dL, AST/ALT \leq 100 IU/L
- G. Ligament instability \leq Grade II
- H. Lower extremity alignment within 5 degrees of the neutral weight bearing axis
- I. No meniscal surgery within the past 3 months and more than 5mm of meniscal rim remaining
- J. Ability and willingness to fully participate in the post-operative rehabilitation program
- K. Subject is informed of the investigational nature of this study, voluntarily agrees to participate in the study, and signs an IRB-approved informed consent prior to performing any of the screening procedures
- L. Body Mass Index (BMI) \leq 35 kg/m²
- 2) Exclusion Criteria
- A. Patients that have been treated previously and are asymptomatic
- B. Avascular necrosis / osteonecrosis
- C. Autoimmune or inflammatory joint disease
- D. History of infection within the past 6 weeks
- E. Surgery or radiation therapy within the past 6 weeks
- F. Serious medical co-morbidities which would otherwise contraindicate surgery, as determined by the investigator
- G. Currently pregnant or nursing
- H. Psychotic diseases, epilepsy, or any history of such diseases

CARTISTEM®

page 20 of 137

CONFIDENTIAL: These all contents herein are the sole property of MEDIPOST Co., Ltd. Any reproduction or distribution of this document without the written consent of MEDIPOST Co., Ltd is prohibited. Copyright © 2017 MEDIPOST Co., Ltd.

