6.5 Dose Escalation

This clinical trial will employ the following dose escalation scheme:

[figure not shown]
A total of 12-18 patients will be enrolled and treated with CARTISTEM[®] for dose limiting toxicity (DLT) evaluation. Initially, 6 patients with lesion sizes of $2 - 5 \text{ cm}^2$ will be assigned to Dosage A and treated with $0.5 - 1.25 \times 10^7$ MSCs; if dose limiting toxicity is not observed at the 3 month time point for the first clinical efficacy evaluation, then another 6 patients with lesion sizes of above 5 cm² will be assigned to Dosage B and treated with more than 1.25 x 10^7 MSCs for further safety evaluation. If a DLT occurs to one or two patients of the group treated with the dosage A, 3 more patients will be assigned to dosage A. If DLT happens to 3 of the patients who were treated with the dosage A or above, this study will be halted and the FDA and IRB will be notified. The Independent Data Monitoring Committee will perform a comprehensive review of safety (see Section 9.1).

CARTISTEM®

page 24 of 137

CONFIDENTIAL: These all contents herein are the sole property of MEDIPOST Co., Ltd. Any reproduction or distribution of this document without the written consent of MEDIPOST Co., Ltd is prohibited. Copyright © 2017 MEDIPOST Co., Ltd.

If no DLT occurs to any of the dosage A patients, another 6 patients with larger defect sizes will be enrolled and assigned to dosage B. In case of no DLT observed, a total of 12 patients will be enrolled for safety and efficacy evaluation. However, 18 patients could be enrolled if DLT occurs to two patients. If DLT occur 3 or more patients treated with Dosage B, this study will be halted and the FDA and IRB will be notified. The Independent Data Monitoring Committee will perform a comprehensive review of safety (see Section 9.1).

CARTISTEM®

page 25 of 137

CONFIDENTIAL: These all contents herein are the sole property of MEDIPOST Co., Ltd. Any reproduction or distribution of this document without the written consent of MEDIPOST Co., Ltd is prohibited. Copyright © 2017 MEDIPOST Co., Ltd.

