6.6 Definition of Maximum Permissible Dose and Method of Dose Escalation

Dose Limiting Toxicity (DLT): DLT is defined as toxicity or events of Grade 3 or higher (80 points or higher against pain) in two or more events at the surgery site among swelling, tenderness, range of motion, and pain in any one visit. DLT is also defined as adverse drug reaction of Grade 3 or higher in the Common Toxicity Criteria Adverse Events (CTCAE), Version 4.0, with the exception of the following events and that they are unresolved for 7 consecutive days, despite medical interventions:

- ✓ Abnormal results in lab test (Acidosis, Hyponatremia, Hyperbilirubinemia, etc.)
- ✓ Fatigue, defined as not relieved by rest; limiting self-care ADL
- ✓ Pain, defined as severe pain; limiting self-care ADL
- ✓ Headache, defined as severe pain in various parts of the head, limiting self-care ADL Fever, defined as > 40.0 degrees C (> 104.0 degrees F) for > 24 hours

Maximum Tolerated Dose (MTD): If DLT occurs in 2 or fewer patients at the Dosage B level, the MTD will be Dosage B. If DLT occurs in 3 or more patients treated with Dosage B then the MTD will be Dosage A. If DLT occurs in 3 patients treated with Dosage A then the MTD will not have been determined in this study design.

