8.4.6 IKDC Score

page 38 of 137

CONFIDENTIAL: These all contents herein are the sole property of MEDIPOST Co., Ltd. Any reproduction or distribution of this document without the written consent of MEDIPOST Co., Ltd is prohibited. Copyright © 2017 MEDIPOST Co., Ltd

The subjects will undergo a self-assessment of knee function using IKDC subjective knee evaluation score before and after the drug administration in order to determine the efficacy of the investigational product. The IKDC assessment will be performed at the 4, 8, 12, 24 weeks and 12 and 24 months after the drug treatment in an exploratory fashion but the IKDC score from the 12 month time point will be used as a primary result of the post-operative change.

8.4.7100-mm VAS Evaluation

The subjects will undergo a self-assessment of joint pain using 100 mm VAS before and the 2, 4, 8, 12, 24 weeks and 12 and 24 months after the drug administration for the efficacy evaluation. Use of NSAIDs must be discontinued for 6 weeks prior to treatment and may be resumed following the treatment. Use of NSAIDs and any other analgesics must be discontinued for 48 hours and 24 hours, respectively, prior to VAS evaluation at Weeks 4, 8, 12, and 24, and Months 12 and 24. Patient may be allowed to take analgesics within 24 hours prior to VAS evaluation at Week 2.

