10.3 Analysis of Efficacy Variables and Statistical Evaluation

10.3.1 Efficacy Variables

Data such as subjective knee function of each category will presented using criteria for the IKDC, the Lysholm score and the KOOS assessment, and the improvement level of pain will be analyzed using the 100-mm VAS. Structural information will be gained through the use of high-resolution (1.5 or 3 Tesla) magnetic resonance imaging (MRI) with cartilage-specific sequences (T2-mapping).

✓ Primary efficacy endpoint: post-operative change in subjective knee function will be obtained from the IKDC score at the 12-month time point as the primary

CONFIDENTIAL: These all contents herein are the sole property of MEDIPOST Co., Ltd. Any reproduction or distribution of this document without the written consent of MEDIPOST Co., Ltd is prohibited. Copyright © 2017 MEDIPOST Co., Ltd

efficacy endpoint.

- ✓ Secondary efficacy endpoint: the Lysholm Score and the KOOS score will be used as the secondary efficacy endpoint to measure post-operative change of the knee function.
- ✓ Improvement degree of joint pain will be measured using a 100-mm VAS (Visual Analogue Scale).
- ✓ Grade of the cartilage regeneration and morphological constitution of the cartilage repair area will be assessed using high-resolution (1.5 or 3 Tesla) magnetic resonance imaging (MRI).

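### The pain-scale form asks about pain in the knee or knees rather than the treated knee, so the secondary pain endpoint does not isolate the treated joint in patients with bilateral pain

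*Combined protocol and SAP*

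**What the plan says.** The instruction printed after the Lysholm form in Appendix 2 tells the patient to mark a line for the "amount of pain you have had in your knee(s) the past 24 hours". It is the only pain-scale instruction in the documents.

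The body of the protocol does not narrow it:

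- Section 8.4.7 calls for a "self-assessment of joint pain using 100 mm VAS" before treatment and at Weeks 2, 4, 8, 12 and 24 and Months 12 and 24, for the efficacy evaluation.
- Section 10.3.1 says "Improvement degree of joint pain will be measured using a 100-mm VAS". The synopsis lists pain on the VAS among the secondary efficacy parameters.
- Section 6.2, inclusion E, requires joint pain of 20 to 60 mm "on VAS (Visual Analog Scale) at the time of Screening".
- Section 6.6 counts a local-sign DLT when two or more of four signs reach the limit "at the surgery site among swelling, tenderness, range of motion, and pain in any one visit". For pain the limit is 80 points. No instrument is named.

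Section 6.2 requires one intended-to-treat defect. It admits defects from ageing and degenerative disease, sets no upper age limit, and has no criterion on pain in the opposite knee.

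**The concern.** A patient whose two knees both hurt has no way to give one mark for both that is also a measure of the treated joint. Patients will resolve this differently, some by marking the worse knee, some by blending, and some by scoring the operated knee regardless. The score then means different things in different patients, and nothing on the record shows which rule was used.

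The wording is also out of step with the rest of the protocol. The Lysholm items and nearly all the IKDC and KOOS items are phrased for a single knee, one KOOS item refers to the injured knee, and the exclusion on recent injections names the affected knee. The DLT definition is tied to the operated site. Only the pain-scale instruction invites an answer covering both knees.

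What is at stake is the validity of the change in joint pain. There is no reference arm, and the cohorts compared by t-test under 10.3.2 have about 6 patients each, so a single distorted score carries visible weight.

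**Working it through.** The plan gives no figure to reproduce. Section 6.3 declines a formal power calculation, and the documents state no expected pain change, standard deviation or frequency of bilateral pain. All scores below are therefore assumed. The cohort size of 6 comes from 6.3.

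**Scoring rules.** Let T be pain in the treated knee and C pain in the other knee.

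- Worse-knee answer: R = max(T, C)
- Average answer: R = (T + C)/2

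**Main illustration.** T goes from 50 to 20 mm and C stays at 50 mm.

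- Treated knee: 20 - 50 = -30 mm
- Worse knee: max(20, 50) - max(50, 50) = 50 - 50 = 0 mm
- Average: (20 + 50)/2 - (50 + 50)/2 = 35 - 50 = -15 mm

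**Sensitivity to the other knee**, with the same treated-knee change of -30 mm and C constant:

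| C (mm) | Worse-knee change | Average change |
|---|---|---|
| 20 | 20 - 50 = -30 | 20 - 35 = -15 |
| 40 | 40 - 50 = -10 | 30 - 45 = -15 |
| 50 | 50 - 50 = 0 | 35 - 50 = -15 |

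A worse-knee answer does no harm while the other knee stays at or below the treated knee's final score; above that it removes part or all of the change. An average answer always halves the change when C is constant.

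**Effect on a cohort mean of 6.** One worse-knee answer at C = 50 shifts the mean by (0 - (-30))/6 = 5 mm. One average answer shifts it by (-15 - (-30))/6 = 2.5 mm.

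**Entry and DLT, only if this form is the instrument used there.**

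- Entry: T = 10 and C = 40 lies outside 20 to 60 mm on the treated knee, but scores 40 (worse knee) or 25 (average) and passes.
- DLT pain component: T = 40 and C = 85 scores 85 on the worse-knee rule and reaches 80 points, although the treated knee does not. T = 85 and C = 20 scores (85 + 20)/2 = 52.5 on the average rule and misses it.

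**The case against.** The strongest reply is that this touches only a secondary, exploratory measure. Primary efficacy is the IKDC score at 12 months, no decision rule uses VAS improvement, and pain is also captured by IKDC, Lysholm and KOOS. That is correct and limits the weight of the point. It does not make the VAS score a measure of the treated knee.

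A second reply is that the printed scale is not in the available text, so a left or right label on it cannot be ruled out. This stands as a caveat. The instruction itself is intact and covers either or both knees.

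A reader might infer more: that contralateral pain can decide eligibility, produce a DLT, or push the trial towards the rule "If DLT happens to 3 of the patients who were treated with the dosage A or above, this study will be halted". The documents do not support that as stated.

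- **DLT.** Section 6.6 names no instrument for the 80 points. Section 9.1 lists pain with swelling, tenderness and range of motion under physical examination, and 8.4.7 gives the VAS an efficacy purpose only. The 100-mm VAS is the only pain measure set out on a 100-point scale, so the link is plausible, but it is inferred. Events must be at the surgery site, so a site applying that strictly would discount the other knee. Pain alone cannot make a local-sign DLT, because a second sign is required. No misclassification rate can be drawn from the documents, so I attach no halting probability.
- **Entry.** Nothing says this form is the Screening instrument. The VAS row of the flow chart, as far as it is legible, starts at Baseline. The investigator also judges eligibility with the target defect identified.
- **Loading of the opposite leg.** It is tempting to argue that six weeks of touch-down weight-bearing raises pain in the other knee. Section 11 allows full weight-bearing in a locked brace for trochlear defects, and the documents do not say that opposite-knee pain rises.

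**Conclusion.** The point holds for the joint-pain efficacy measure. The form asks for one score across one or both knees, no passage restricts it to the treated knee, and bilateral pain is not excluded. In a patient with bilateral pain the recorded change can be diluted. In the main illustration -30 mm becomes 0 or -15 mm, and a 6-patient cohort mean moves by 5 or 2.5 mm for each such patient.

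Those sizes rest on assumed scores, on a constant other knee, and on the patient following the form literally. How many patients this would affect is unknown. For entry and DLT the conclusion goes no further than this: the documents do not say which pain measure applies, and the form's wording does not match the site-specific wording of 6.6. The primary IKDC endpoint is not affected.

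**What to change.** Reword the instruction to ask about pain in the treated (study) knee, with the side pre-printed. Use that form at every visit where the VAS is collected, and add one sentence to 8.4.7 saying that the VAS is scored for the study knee.

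Separately, reconcile the form with the joint-pain wording in 6.2 and the surgery-site wording in 6.6, and have the sponsor state which pain measure each relies on. The choice of instrument and threshold there is the sponsor's and is not proposed here.

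The cost is a one-line change to a patient form and a few protocol sentences. No visit, procedure, dose or sample size changes. Scores already marked on the current form cannot later be separated by knee, so any such scores should be identified by form version in the listings.

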APPENDIX 3. KOOS KNEE SCORE

Knee injury and Osteoarthritis Outcome Score (KOOS), English version LK1.0

-				
D	-		n	
-	a	L		

P1. How often	do you experience	knee pain?		
Never	Monthly	Weekly	Daily	Always

What amount of knee pain have you experienced the **last week** during the following activities?

P2. Twisting/pive None	oting on your kr Mild D	Moderate	Severe	Extreme
P3. Straightening None	knee fully Mild □	Moderate	Severe	Extreme
P4. Bending knee None	fully Mild		Severe	Extreme
P5. Walking on fl None	at surface Mild	Moderate	Severe	Extreme
P6. Going up or d None	lown stairs Mild	Moderate	Severe	Extreme
P7. At night while None	e in bed Mild	Moderate	Severe	Extreme
P8. Sitting or lyin None	g Mild	Moderate	Severe	Extreme
P9. Standing upri None	ght Mild □	Moderate	Severe	Extreme

Function, daily living

The following questions concern your physical function. By this we mean your ability to move around and to look after yourself. For each of the following activities please indicate the degree of difficulty you have experienced in the **last week** due to your knee.

A1. Descending	stairs			
None	Mild	Moderate	Severe	Extreme
A2 Assauding	taina			
A2. Ascending s		2.2		
None	Mild	Moderate	Severe	Extreme

CARTISTEM®

page 55 of 137

For each of the following activities please indicate the degree of difficulty you have experienced in the **last week** due to your knee.

A3. Risin None	g from sitting Mild	Moderate	Severe	Extreme
A4. Stand None		Moderate	Severe	Extreme
A5. Bend None	ing to floor/pick up Mild □	an object Moderate	Severe	Extreme
A6. Walk None	ing on flat surface Mild	Moderate	Severe	Extreme
A7. Getti None	ng in/out of car Mild	Moderate	Severe	Extreme
A8. Goin None	g shopping Mild	Moderate	Severe	Extreme
A9. Puttin None	ng on socks/stockin Mild	gs Moderate □	Severe	Extreme
A10. Risi None	ng from bed Mild	Moderate	Severe	Extreme
A11. Tak None	ing off socks/stocki Mild □	ngs Moderate □	Severe	Extreme
A12. Lyin None	ng in bed (turning o Mild	ver, maintaining kn Moderate	nee position) Severe	Extreme
A13. Gett None	ing in/out of bath Mild	Moderate	Severe	Extreme
A14. Sitti None		Moderate	Severe	Extreme
A15. Gett None	ing on/off toilet Mild	Moderate	Severe	Extreme
CARTISTEM®				page

page 56 of 137

For each of the following activities please indicate the degree of difficulty you have experienced in the **last week** due to your knee.

A16. Heavy don	nestic duties (mo	oving heavy boxes,	scrubbing floors	, etc)
None	Mild	Moderate	Severe	Extreme
A17. Light dom	estic duties (coo	king, dusting, etc)		
None	Mild	Moderate	Severe	Extreme

Function, sports and recreational activities

The following questions concern your physical function when being active on a higher level. The questions should be answered thinking of what degree of difficulty you have experienced during the **last week** due to your knee.

SP1. Squatting None	Mild	Moderate	Severe	Extreme
SP2. Running None	Mild	Moderate	Severe	Extreme
SP3. Jumping None	Mild	Moderate	Severe	Extreme
SP4. Twisting/piv None	voting on your i Mild D	njured knee Moderate	Severe	Extreme
SP5. Kneeling None	Mild	Moderate	Severe	Extreme
Quality of Life				
Q1. How often ar Never	e you aware of Monthly	your knee problem Weekly □	? Daily	Constantly
Q2. Have you mo	dified your life			activities
		style to avoid poter	ntially damaging	acuvities
to your knee? Not at all		Moderately	Severely	
to your knee? Not at all	Mildly	Moderately	Severely	Totally
to your knee? Not at all Q3. How much ar Not at all	Mildly Mildly re you troubled Mildly □	Moderately with lack of confide Moderately	Severely contact in your kne Severely	Totally D e? Extremely

Thank you very much for completing all the questions in this questionnaire.

CARTISTEM®

page 57 of 137

Common Terminology Criteria for Adverse Events (CTCAE) Version 4.0

U.S.DEPARTMENT OF HEALTH AND HUMAN SERVICES National Institutes of Health National Cancer Institute

CARTISTEM®

page 58 of 137

Common Terminology Criteria for Adverse Events v4.0 (CTCAE) -----

	Publish Date: May 28, 2009	
Quick Reference The NCI Common Terminology Criteria for Adverse Events is a descriptive terminology which can be utilized for Adverse Event (AE) reporting. A grading (severity) scale is provided for each AE term. Commonents and Oreanization SOC System Organ Class, the highest level of the MedDRA hierarchy, is identified by anatomical or physiological system, etiology, or purpose (e.g., SOC Investigations for laboratory test results). CTCAE terms are grouped by MedDRA Primary SOCs. Within each SOC, AEs are listed and accompanied by descriptions of severity (Grade). CTCAE Terms An Adverse Event (AE) is any unfavorable and unintended sign (including an abnormal laboratory finding), symptom, or disease temporally associated with the use of a medical treatment or procedure that may or may not be considered related to the medical treatment or procedure. An AE is a term that is a unique representation of a specific event used for medical documentation and scientific analyses. Each CTCAE v4.0 term is a MedDRA LLT (Lowest Level Term).	Grades Grade refers to the severity of the AE. The CTCAE displays Grades 1 through 5 with unique clinical descriptions of severity for each AE based on this general guideline: Grade 1 Mild; asymptomatic or mild symptoms; clinical or diagnostic observations only; intervention not indicated. Grade 2 Moderate; minimal, local or noninvasive intervention indicated; limiting age-appropriate instrumental ADL ⁴ . Grade 3 Severe or medically significant but not immediately life-threatening; hospitalization indicated; disabling; limiting self care ADL ⁴⁴ . Grade 4 Life-threatening consequences; urgent intervention indicated. Grade 5 Death related to AE.	"Self care ADL refer to bathing, dressing and undressing, feeding self, using the toilet, taking medications, and not bedridden.

1 CTCAE v4.0 incorporates certain elements of the MedDRA terminology. For further details on MedDRA refer to the MedDRA MSSO Web site [http://www.meddiamsso.com].

page 59 of 137

	В	lood and lymphatic syst	em disorders		
			Grade		
Adverse Event	1	2	3	4	5
Anemia	Hemoglobin (Hgb) < LLN - 10.0 g/dL; < LLN - 6.2 mmol/L; <lln -
100 g/L</lln>	2	Hgb <8.0 - 6.5 g/dL; <4.9 - 4.0 mmol /L; <80 - 65 g/L; transfusion indicated	Life-threatening consequences; urgent intervention indicated	Death
	ized by an reduction in the amount (th, palpitations of the heart, soft syst	NAR 7.4 1993) D.588940	65.005 States	ay include pallor of the skin and m	nucous
Bone marrow hypocellular	Mildly hypocellular or <= 25 % reduction from normal cellularity for age	Moderately hypocellular or >25 -	24	Aplastic persistent for longer than 2 weeks	Death
	ized by the inability of the bone man	12		1	
Disseminated intra vascular coagulation		Laboratory findings with no bleeding	Laboratory findings and bleeding	Life-threatening consequences; urgent intervention indicated	Death
	ized by systemic pathological activa r is depleted of platelets and coagula	085 - 789702	which results in dot formation thr	oughout the body. There is an incr	nease in the
Febrile neutropenia		-	Present	Life-threatening consequences; urgent intervention indicated	Death
Definition: A disord er character	ized by a decrease in neutrophils as	ssociated with fever.			2
Hemolysis	Lab oratory evidence of hemolysis only (e.g., direct antiglobulin test; DAT; Coombs'; schistocytes; decreased haptoglobin)	Evidence of hemolysis and >=2 gm decrease in hemoglobin, no transfusion	Transfusion or medical intervention indicated (e.g., steroid s)	Life-threatening consequences; urgent intervention indicated	Death
Definition: A disord er character	ized by laboratory test results that in	ndicate widespread erythrocyte œ	Il membrane destruction.		35 35
Hemolytic uremic syndrome	Evidence of RBC destruction (schistocytosis)without dinical consequences		Laboratory indings with clinical consequences (e.g., renal insufficiency, petechiae)	Life-threatening consequences, (e.g., CNS hemorrhage or thrombosis/embolism or renal failure)	Death
Definition: A disord er character	ized by a form of thrombotic microar	ngiopathy with renal failure , hemo	lytic anemia, and severe thromboo	cytopenia.	50) 19
Leukocytosis Doficition: A disorder obarrator	- ized by laboratorytest results that ir	diate to increased purphy of u	>100 000/mm3	Clinical manifestations of leucostasis; urgent intervention indicated	Death
Lymph node pain	Mild pain	Moderate pain ; limitin g	Severe pain; limiting self care	3	5
	· · · · · · · · · · · · · · · · · · ·	instrumental ADL	ADL		ł.
Spleen disorder	ized by a sensation of marked disco Incidental Indings (e.g., Howell- Jolly bodies); mild degree of thrombocytosis and leukocytosis	Prophylactic antibiotics indicated		Life-threatening consequences; urgent intervention indicated	Death
Definition: A disord er of the spl	The second	Ê	i Touristantina anna anna anna anna anna anna an		-
Thrombotic thrombocytopenic purpura	Evidence of RBC destruction (schistocytosis)without dinical consequences		Laboratory findings with clinical consequences (e.g., renal insufficiency, petechiae)	Life-threatening consequences, (e.g., CNS hemorrhage or thrombosis/embolism or renal failure)	Death
	ized by the presence of microangiop sual disturbances. It is an acute or s	572 0.0 (Strike	cytopenic purpura, fever, renal abr	normalities and neurological abnor	malities suc
Blood and lymphatic system disorders - Other, specify	Asymptomatic or mild symptoms; dinical or diagnostic observations only; intervention not indicated	Moderate; minimal, local or nonin vasive intervention indicated; limiting age- appropriate instrumental ADL	Severe or medically significant but not immediately life- threatening; hospitalization or prolongation of existing hospitalization in dicated; disabling; limiting self care ADL	Life-threatening consequences; urgent intervention in dicated	Death

CTCAE 4.0 - May 28, 2009 : 8 bod and tympilatic system disorde s -3

CARTISTEM®

page 60 of 137

a to myocardial infa valvular h or without mild gitation or vaging in a ortic valve funct ystole; non-urgent gement indicated thmia without cardii c, intervention not	arction. Asymptomatic; moderate regurgitation or stenosis by timaging tion or structure. ac electrical activity. Typically, this Non-urgent medical intervention indicated Non-urgent medical intervention indicated	abnormal, hemodynamically stable fium secondary to coronary artery Symptomatic; severe regungitation or stenosis by imaging; symptoms controlled with medical intervention s is accompanied by cessation of ft Symptomatic and incompletely controlled medically, or controlled with device (e.g., pacemaker), or ablation entricular response due to multiple Symptomatic and incompletely controlled medically, or controlled medically, or	4 Symptomatic, unstable angina and/or acute myo cardial infarction, cardiao enzymes abnormal, hemodynamically unstable rdisease. The clinical presentation Life-threatening consequences; urgent intervention indicated (e.g., valve replacement, valvuloplasty) Life-threatening consequences; urgent intervention indicated the pumping function of the heart. Life-threatening consequences; urgent intervention indicated he pumping function of the heart. Life-threatening consequences; urgent intervention indicated reentry circuits. The rhythm distur Life-threatening consequences; urgent intervention indicated	Death Death Death bance
d symptoms related a to myocardial infa svalvular h or without mild gitation or laging in a ortic valve funct gement indicated thmia without cardii c, intervention not	Symptomatic, progressive angina; cardia o enzymes normal; hemodynamically stable d to acute ischemia of the myocard arction. Asymptomatic; moderate regungitation or stenosis by imaging tion or structure. ac electrical activity. Typically, this Non-urgent medical intervention indicated Non-urgent medical intervention indicated	Symptomatic, unstable angina and/or acute myocardial infarction, cardiae enzymes abnormal, hemodynamically stable fium secondary to coronary artery Symptomatic; severe regungitation or stenosis by imaging; symptoms controlled with medical intervention sis accompanied by cessation of th Symptomatic and incompletely controlled medically, or controlled with device (e.g., pacemaker), or ablation entricular response due to multiple Symptomatic and incompletely controlled medically, or controlled with device (e.g., pacemaker), or ablation	Symptomatic, unstable angina and/or acute myo cardial infarction, cardiac enzymes abnormal, hemodynamically unstable disease. The clinical presentation Life-threatening consequences; urgent intervention indicated (e.g., valve replacement, valvuloplasty) Life-threatening consequences; urgent intervention indicated he pumping function of the heart. Life-threatening consequences; urgent intervention indicated reentry circuits. The rhythm distur Life-threatening consequences;	Death covers a Death Death bance
a to myocardial infa valvular h or without mild gitation or vaging in a ortic valve funct ystole; non-urgent gement indicated thmia without cardii c, intervention not	angina; cardia c enz yme s normal; hemodynamically stable d to acute ischemia of the myo card arction. Asymptomatic; moderate regurgitation or stenosis by imaging tion or structure. ac electrical activity. Typically, this Non-urgent medical intervention indicated Non-urgent medical intervention indicated	and/or acute myocardial infarction, cardiac enzymes abnormal, hemodynamically stable dium secondary to coronary artery Symptomatic; severe regurgitation or stenosis by imaging; symptoms controlled with medical intervention : is accompanied by cessation of th Symptomatic and incompletely controlled medically, or controlled with device (e.g., pacemaker), or ablation entricular response due to multiple Symptomatic and incompletely controlled medically, or controlled medically, or controlled medically, or controlled medically, or	and/or acute myo cardial infarction, cardiao enzymes abnormal, hemodynamically unstable disease. The clinical presentation Life-threatening consequences; urgent intervention indicated (e.g., valve replacement, valvuloplasty) Life-threatening consequences; urgent intervention indicated he pumping function of the heart. Life-threatening consequences; urgent intervention indicated reentry circuits. The rhythm distur Life-threatening consequences;	co vers a Death Death Death bance
a to myocardial infa valvular h or without mild gitation or vaging in a ortic valve funct ystole; non-urgent gement indicated thmia without cardii c, intervention not	arction. Asymptomatic; moderate regurgitation or stenosis by timaging tion or structure. ac electrical activity. Typically, this Non-urgent medical intervention indicated Non-urgent medical intervention indicated	Symptomatic; severe regurgitation or stenosis by imaging; symptoms controlled with medical intervention s is accompanied by cessation of ft Symptomatic and incompletely controlled medically, or controlled with device (e.g., pacemaker), or ablation entricular response due to multiple Symptomatic and incompletely controlled medically, or controlled medically, or	Life-threatening consequences; urgent intervention indicated (e.g., valve replacement, valvuloplasty) Life-threatening consequences; urgent intervention indicated he pumping function of the heart. Life-threatening consequences; urgent intervention indicated reentry circuits. The rhythm distur Life-threatening consequences;	Death Death Death bance
h or without mild gitation or laging stole; non-urgent gement indicated thmia without cardii c, intervention not thmia without disce	regurgitation or stenosis by imaging tion or structure. ac electrical activity. Typically, this Non-urgent medical intervention indicated rnible P waves and an irregular ve Non-urgent medical intervention indicated	regurgitation or steinosis by imaging; symptoms controlled with medical intervention is accompanied by cessation of ft Symptomatic and incompletely controlled medically, or controlled with device (e.g., pacemaker), or ablation entricular response due to multiple Symptomatic and incompletely controlled medically, or controlled with device (e.g.,	urgent intervention indicated (e.g., valve replacement, valvuloplasty) Life-threatening consequences; urgent intervention indicated he pumping function of the heart. Life-threatening consequences; urgent intervention indicated reentry circuits. The rhythm distur Life-threatening consequences;	Death Death bance
